12.5 Secondary Analysis

For secondary endpoint, change in measurement of dermal thickness (screening evaluations to Month 12), as measured by caliper skin fold thickness, the mean response of the BioBridge recipients to ALNT only participants will be compared. The statistical methods used for the secondary endpoints will follow the methods used for the primary endpoints.

12.5.1 Analysis Population

N/A; no subset analysis

12.5.2 Analysis Plan

The same analysis plan will be used for secondary endpoint as was used for the primary endpoint.

Exploratory Endpoints and Outcomes

L-Dex: Multiple frequency bioelectrical impedance analysis (MFBIA) will be performed with the impedance device. This tool utilizes multiple frequency electrical current (1 kHz to 500 kHz) to determine extracellular fluid (ECF) volume. At low frequency (< 50 kHz) current does not penetrate the cell membrane into the intracellular space, as opposed to high frequency current (> 200 kHz). As a result, intracellular and extracellular volumes can be measured separately.²⁶⁻²⁹ An impedance value, the L-Dex score, can then be calculated which is inversely proportional to the fluid content of the compartment. This noninvasive approach has been evaluated for its capacity to detect subtle disease and to predict the advent of clinically relevant edema.³⁰⁻³² MFBIA is predicted to have the requisite sensitivity and specificity to detect the feasibly small differences in retained interstitial fluid that might discriminate the therapeutic responses of the treated patients. MFBIA will be measured at screening evaluations and at each follow-up visit. A standardized quantitative score, the L-Dex score, will be generated for the ipsilateral and contralateral limb.³⁰ This will be done as specified in the treatment plan above. It has been established that a 10-point change in L-Dex score corresponds to 3 standard deviation (SD) range from the mean.^{30,31} See Figure 3 below.

[figure not shown]

Figure 3. 10-point change in L-Dex score corresponds to 3 SD range from the mean (obtained from ImpediMed L-DEX technical bulletin).^{30,31}

Change in lymphatic flow function by serial radionuclide lymphoscintigraphy (LSG):

Significant improvement in the scintigraphic uptake of the radionuclide in a defined ROI within the proximal LN drainage pathway (axilla); improvement in the reduction of scintigraphic density in a defined ROI for dermal backflow, and improvement in the disappearance rate constant from the injection site.

Change in the lymphedema Quality of Life (LymQOL) score:

Greater improvement in the aggregate score on the validated instrument.

Change in quantifiable skin histopathology, optional for control group: greater reduction in dermal-epidermal thickness, greater reduction in dermal collagen thickness, and greater improvement in lymphatic vascular size and density.

12.6 Sample Size

12.6.1 Accrual estimates

[name] directs a national referral center for lymphatic disorders and approximately 600 new patients with clinically significant lymphedema are seen in on a yearly basis. Some of these patients are referred from the breast clinic but majority comes from local and regional physician offices. [name] performs 15 to 19 vascularized lymph node transfers yearly (of subjects who meet the eligibility criteria). We expect to be able to accrue subjects to this study within 48 months. Once study has been approved and is enrolling, in order to facilitate enrollment in the allotted time frame, we plan to add 3 subsites in order to meet accrual goal.

12.6.2 Sample size justification

In order to successfully test the null hypothesis, we have performed sample size calculations. After careful review of the published literature, we are able to identify a study in which the effect of the surgery on limb circumference (as a surrogate for limb volume) has been quantitated and for which a published effect size of 51% reduction in limb volume with standard deviation of 19% is available for standard care.³³ We have utilized this published value (SD = 19%) to calculate our power in relationship to the detectable alternative. If we allow for a 4:1 ratio of VLNT in intervention: control arms, and successful project completion of the protocol by 48 VLNT with BioBridge subjects and 12 controls (VLNT without BioBridge), we have utilized an alpha = 0.05 and a power = 0.9 to predict that the detectable alternative would be \pm 20%.

12.6.3 Effect size justification

An additional volume reduction of 20% ascribable to the BioBridge (versus VLNT only) would represent a substantial and clinically relevant amelioration in the surgical outcome when compared to current, standard VLNT without BioBridge supplementation. This magnitude of treatment differential has been demonstrated for the BioBridge in lymphedema, both in our published large animal study as well as in pilot observations of the surgical effect of the BioBridge performed in the Dominican Republic (unpublished observations).

12.7 Criteria for future studies

Future studies are not planned at this time.

APPENDIX A: Participant Eligibility Checklist

Protocol Information

Protocol Name: Prospective Evaluation of a Surgical Solution for Breast Cancer-Associated Lymphedema

E-Protocol number: IRB-37161 / BRS0095

Principal Investigator: [name]

Participant Information

Participant Name/ID:

Date of Birth:

Gender: Male Female

Study Information

SRC-approved IRB-approved Contract signed

Inclusion/Exclusion Criteria

Inclusion Criteria (From IRB-approved protocol)	Yes	No	Supporting Documentation
1. Ages 18 to 75 years (inclusive)			
2. Eastern Cooperative Oncology Group (ECOG) Performance Status 0 to 2			
3. Life expectancy > 2 years			
4. Acquired (secondary) upper limb lymphedema (secondary to breast cancer treatment)			
5. The participant must be eligible for surgical intervention.			
6. Swelling of 1 limb that is not completely reversed by elevation or compression			
7. Stage II or greater lymphedema at screening, based on the International Society of Lymphology (ISL) staging system			
8. Participants must have no evidence of disease (NED), have completed breast cancer therapy 3 years prior to enrollment; use of endocrine therapy is allowed.			
9. Completion of a full course of complete decongestive therapy (CDT), according to ISL guidelines at least 8 weeks prior to screening, including use of compression garments for at least 8 weeks without change in regimen			

10. Willingness to maintain a stable regimen of self-care, including use of compression garments from screening through the entire study duration (through the safety follow-up visit). Self-bandaging, use of nighttime compression garments, and intermittent pneumatic compression devices are allowed, but the procedures and regimens are expected to remain consistent from screening through the entire study duration.			
11. Consistent use of an appropriately-sized compression garment for daytime use.			
12. Two consecutive measurements of limb volume (LV) in the affected arm, taken at least 1 day apart during the screening period, must be within 10% of each other. A maximum of 3 measurements can be taken. Affected limb volume ratio must be > 20% (compared to unaffected limb); volume measurements will be performed and volume ratio will be calculated at S1 and S2 visit.			
13. Evidence of abnormal bioimpedance ratio, if feasible, based upon unilateral disease: L-Dex > 10 units; bioimpedance performed at S1 and S2			
14. Willing and able to comply with all study procedures, including measurement of skin thickness using skin calipers			
15. Willing and able to understand, and to sign a provide written informed consent			
Exclusion Criteria (From IRB-approved protocol)	Yes	No	Supporting Documentation
1. Edema arising from increased capillary filtration will be excluded (venous incompetence).			
2. Inability to safely undergo general anesthesia and/or perioperative care related to vascularized lymph node transfer			
3. Concurrent participation in a clinical trial of any other investigational drug or therapy, regardless of indication, within 1 month before screening or 5 times the drug's half-life, whichever is longer.			
4. Recent initiation of (\leq 8 weeks), or intention to initiate, CDPT or maintenance physiotherapy for lymphedema at any time during the duration of the study			
5. Other medical condition that could lead to acute limb edema, such as (but not limited) to acute venous thrombosis			

6. Other medical condition that could result in symptoms overlapping those of lymphedema in the affected limb (eg, pain, swelling, decreased range of motion)			
7. History of clotting disorder (hypercoagulable state)			
8. Chronic (persistent) infection in the affected limb			
9. Any other infection (unrelated to lymphedema) within 1 month prior to screening			
10. Currently receiving chemotherapy or radiation therapy			
11. Current evidence, or a history of malignancy within the past 3 years (except for non-melanoma skin cancer or cervical cancer in situ treated with curative intent). If the participant has undergone cancer treatment, this must have been completed > 3 years prior to enrollment.			
12. Current evidence of any high risk for recurrence of breast cancer [eg, Stage III or IV; estrogen receptor (ER) / progesterone receptor (PR) / HER-2 negative (ie, "triple-negative") cancer; locally-advanced disease; inflammatory breast cancer; > 3 positive axillary lymph nodes; extracapsular nodal extension; invasive micropapillary breast carcinoma; or if performed, genetic testing, eg, BRCA1; BRCA2; Oncotype DX (high-risk recurrence score); or Mammaprint (poor risk signature) indicating a high risk for breast cancer recurrence			
13. Significant or chronic renal insufficiency (defined as serum creatinine > 2.5 mg/dL or an estimated glomerular filtration rate [eGFR] < 30 mL/min at screening) or requires dialytic support			
14. Hepatic dysfunction, defined as alanine transaminase (ALT) or aspartate transaminase (AST) levels > 3 × upper limit of the normal range (ULN) and/or bilirubin level > 2 × ULN at screening			
15. Absolute neutrophil count < 1500 mm ³ at screening			
16. Hemoglobin concentration < 9 g/dL at screening			
17. Known sensitivity to porcine products			
18. Hypersensitivity to iodine			
19. Pregnancy or nursing			
20. Substance abuse (such as alcohol or drug abuse) within 6 months prior to screening			
21. Any reason (in addition to those listed above) that, in the opinion of the investigator, precludes full participation in the study			

IV. Statement of Eligibility

By signing this form of this trial I verify that this subject is **eligible** / **ineligible** for participation in the study. This study is approved by the Stanford Cancer Institute Scientific Review Committee, the Stanford IRB, and has finalized financial and contractual agreements as required by Stanford School of Medicine's Research Management Group.

Treating Physician Signature

Date

Printed Name

Second Reviewer Signature

Date

Printed Name

Study Coordinator Signature

Date

Printed Name

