2. BACKGROUND

2.1 Study Disease

Lymphedema

Secondary (acquired) lymphedema is a serious, progressive and global disease that develops when the lymphatic system is physically compromised and unable to sufficiently transport interstitial fluid and macromolecules from affected region(s) of the body to the central circulation. In Western countries, it most commonly occurs as a delayed result of cancer treatment, most frequently in survivors of breast and gynecological cancers. In this highly prevalent condition, lymph node extirpation and the associated structural damage to the lymphatic vasculature leads to the inexorable accumulation of interstitial fluid, accompanied by regional compromise of immune function and, ultimately, irreversible structural changes of the affected tissues of the limb(s).¹ Lymphedema is a chronic, debilitating disease with profound functional and psychosocial implications.²

According to the American Cancer Society (ACS), in women there will be an estimated 252,710 new cases of invasive breast cancer, 63,410 of *in situ* breast cancer, and in men, 2,470 cases.²⁴ In 2017, approximately 40,610 women and 460 men are expected to die from breast cancer.

Development of upper extremity (UE) edema following axillary lymph node dissection for breast cancer treatment is the most common manifestation. Conservative estimates place the incidence of UE edema after axillary lymph node dissection at 15-26%.^{3,5-7} Conservative axillary management (SLND) has resulted in reduced incidents of breast cancer related edema.⁸⁻¹⁰

To decrease the risk of recurrence for early-stage breast cancer patients with a positive SLN, radiotherapy is typically recommended. AMAROS trial results showed the rate of lymphedema in patients with early-stage breast cancer with positive SLN, was 15% at 1 year; 13.4% at 3 years; 10.3 at 5 years. Women who had ALND and axillary radiotherapy had the highest rates of lymphedema (25.6% at 1 year; 21% at 3 years; 20.8% at 5 years).¹¹

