4.3 Alternatives

Alternatives to participation in this trial include enrollment in VLNT without the addition of the BioBridge scaffold or standard of care treatments for lymphedema. These include, but are not limited to, compression sleeves or compression devices, decongestive therapy, intermittent pneumatic compression devices. In general, there are 4 types of surgical intervention for lymphedema, as follows.^{35,36,46-48}

Lymphatic Microsurgical Preventive Healing Approach (LYMPHA), aimed at lymphedema prevention, was developed at the University of Genoa.^{37,38} At the time of axillary lymph node dissection, a lymphaticovenous anastomosis (LVA) is performed to restore lymphatic flow. While a comparatively new procedure, for patients undergoing ALND, results have been very promising.³⁹ However, since it is aimed at lymphedema prevention, LYMPHA is not an appropriate alternative for this participant population, since inclusion into this trial requires a diagnosis of lymphedema.

Excisional surgery, suction-assisted protein lipectomy (SAPL), pioneered by [name], is performed for chronic non-pitting lymphedema. SAPL is highly effective at removing the excess solid tissue (hypertrophied adipose tissue) but does not restore lymphatic function. [name], who trained with [name], frequently performs this procedure. Post-operatively, the continuous use (24 hours/day, 7 days/week) of custom compression garments is required. These may need to be frequently replaced in the 1st year after the procedure. Maintenance of reduction is dependent on patient compliance with continuous compression garment use.⁴⁰ SAPL is also not an appropriate alternative, since its aim is removal of excess tissue and not the restoration of lymphatic function.

Microvascular reconstruction with LVA is also performed by [name]. A large study, by Chang, *et al*, noted that LVA, is most effective in early stage lymphedema of the upper extremity. Early volume reduction may be seen in the first postoperative week but maintenance of response is unknown due to short follow-up.⁴¹ Additionally, LVA may not enhance the regional immune impairment that accompanies lymphedema.

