12 months. We will conduct the primary analysis to evaluate whether there is a difference between the treatment and control arms in the volume reduction of the affected limb at 12 months. We will fit the linear mixed effects model below assuming an AR(1) covariance structure. We will evaluate the sensitivity of our assumption about the covariance structure by assuming an unstructured covariance in a sensitivity analysis. Let Y_{ij} represent the reduction in volume of the affected limb for subject i at time j (for $j = 3, 6, 9$, and 12 months), γ_i be the random intercept for subject i , ϵ_{ij} be the error for subject i at time j , trt_i be an indicator for whether subject i is in the BioBridge arm, and $m3_{ij}$; $m6_{ij}$; $m9_{ij}$; $m12_{ij}$ be indicators for whether a measurement on subject i at time j was taken at Month 3; 6; 9; or 12, respectively. To assess whether there is a volume reduction of the affected limb at 12 months, we will test the null hypothesis that $\beta_1 + \beta_7 = 0$ vs the alternative hypothesis of $\beta_1 + \beta_7 \neq 0$.

$$Y_{ij} = \beta_0 + \gamma_i + \beta_1 trt_i + \beta_2 * m6_{ij} + \beta_3 * m9_{ij} + \beta_4 * m12_{ij} + \beta_5 * m6_{ij} * trt_i + \beta_6 * m9_{ij} * trt_i + \beta_7 * m12_{ij} * trt_i + \epsilon_{ij}$$

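### The primary model omits ISL stage, which screening must already judge; adding it as a prespecified covariate is a near-free guard against chance imbalance with only 12 controls, though the gain is unknown

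*Combined protocol and SAP*

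**What the plan says.** **Entry.** Section 3.1.7 and item 7 of the Appendix A checklist set a lower limit on stage and no upper one: "7. Stage II or greater lymphedema at screening, based on the International Society of Lymphology (ISL) staging system". The checklist columns are Yes, No and supporting documentation. The study calendar (section 9) has no row for stage.

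**Randomization.** Sections 3.4 and 12.1.1 describe 4:1 allocation of about 60 patients. Section 3.4 gives blocks of five. Neither names a stratification factor.

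**Primary model.** Section 12.4 states: "We will fit the linear mixed effects model below assuming an AR(1) covariance structure". The equation contains arm, visit indicators, arm-by-visit products and a subject random intercept, with no baseline covariate. The sensitivity analyses change the covariance structure, the population or the missing-data handling; none brings in stage. Section 12.3 plans no descriptive or exploratory analysis. Section 12.5 applies the same methods to the secondary endpoint.

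**Stage and response.** Section 2.1 says the disease leads to "ultimately, irreversible structural changes of the affected tissues of the limb(s"). Section 4.3 says of lymphaticovenous anastomosis (LVA), a different operation, that it "is most effective in early stage lymphedema of the upper extremity". No passage gives VLNT outcome by stage.

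**The concern.** The endpoint is the percentage of excess limb volume removed. Section 4.3 separates removal of excess solid tissue from restoration of lymphatic function, and VLNT aims at the second. It is therefore plausible, though not shown, that a limb with more fixed tissue change responds less in either arm. Stage is also not the same thing as baseline excess volume: two limbs with equal excess can be at different stages.

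With 12 controls, a few extra later-stage patients in one arm would move the Month 12 contrast, and the planned analyses have no term to account for it. Any variance due to stage would sit mainly in the subject random intercept and would enter the standard error of the Month 12 treatment contrast. The trial is open-label, so a covariate chosen after results are seen would carry little weight. A stage value not captured before surgery may be hard to recover.

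**Working it through.** **1. The plan's own figure.** Inputs from 12.6.2: SD 19 points ("a published effect size of 51% reduction in limb volume with standard deviation of 19% is available for standard care"), 48 and 12 completers, alpha 0.05, power 0.9. The test in 12.4 is two-sided.

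- SE = 19 × √(1/12 + 1/48) = 19 × 0.3227 = 6.13 points.
- Detectable difference, normal approximation: (1.960 + 1.282) × 6.13 = 19.9 points. Power at 20 points is 0.903.
- Noncentral t, 58 df: detectable difference 20.2 points, power at 20 points 0.894.

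The stated 20% reproduces without any covariate. The t figures are the reference below.

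**2. Chance imbalance.** Assumptions, not in the documents: p is the share of patients later than Stage II, and D is how many points less they respond. The shift in the unadjusted estimate is D × (difference in later-stage share between arms).

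- With p = 0.3 (18 of 60), six or more later-stage controls leaves at most 12 on BioBridge: 6/12 − 12/48 = 25 percentage points or more. By the hypergeometric distribution this happens in about 9% of randomizations.
- A 25-point imbalance shifts the estimate by 0.25 × 10 = 2.5 points (D = 10) or 0.25 × 20 = 5 points (D = 20), against an SE of 6.13 and a 20-point target.

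**3. Validity of the unadjusted test.** This was checked with 10,000 simulated Month 12 two-arm comparisons per scenario, at p = 0.3 with no true effect.

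- Overall false-positive rate: 4.9% (D = 10) and 5.1% (D = 20), with a mean estimate near zero.
- Among the roughly 10% of trials with at least 20 points more later-stage controls: 7.0% (D = 10) and 11.4% (D = 20).

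**4. Effect of adjusting.** Hold the total SD at 19.

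- Residual SD s = √(361 − p(1 − p)D²).
- Adjusted SE = s × 0.3227 × √(1 + 1/56), the last factor allowing for one estimated covariate.
- Power at 20 points: noncentral t, 57 df, noncentrality 20 / adjusted SE.

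Example, p = 0.3 and D = 20: p(1 − p)D² = 0.21 × 400 = 84, which is 84/361 = 23% of the variance. Then s = √277 = 16.64, the adjusted SE is 5.42 and the noncentrality is 3.69. Power is 0.952.

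| Later than II (p) | D (points) | Residual SD | Power at 20 | Detectable difference |
|---|---|---|---|---|
| No adjustment | – | 19.0 | 0.894 | 20.2 |
| any | 0 | 19.0 | 0.888 | 20.4 |
| 0.1 | 5 | 18.9 | 0.890 | 20.3 |
| 0.1 | 10 | 18.8 | 0.896 | 20.1 |
| 0.3 | 5 | 18.9 | 0.893 | 20.3 |
| 0.3 | 10 | 18.4 | 0.906 | 19.8 |
| 0.3 | 15 | 17.7 | 0.926 | 19.0 |
| 0.3 | 20 | 16.6 | 0.952 | 17.9 |
| 0.5 | 20 | 16.2 | 0.962 | 17.3 |

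There is no gain when stage explains less than about 2% of the variance. The D = 0 row gives the cost if stage is not prognostic at all: 0.894 − 0.888 = 0.006 of power.

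**The case against.** The strongest reply is that the documents do not establish stage as prognostic for VLNT. The one stage-response sentence in 4.3 is about LVA and about early disease, whereas this trial starts at Stage II. Section 2.1 describes natural history, not response to surgery. Other entry rules may keep the later-stage share low: L-Dex above 10 where feasible (3.1.13), surgical eligibility (3.1.5) and planned VLNT (10.1.1). All of this stands, and it is why the gain can only be given as a range that includes a slight loss.

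A reader might infer that leaving stage out biases the BioBridge estimate or inflates the type I error. It does not. Over randomizations the estimate is centred correctly and the error rate is about 5%. The shifts in step 2 are already inside the unadjusted interval (half-width 1.96 × 6.13 = 12.0 points), so shift and lost precision are one quantity, not two harms. A reader might also infer that the sample size is wrong; step 1 shows it is not.

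Two technical limits also stand. The calculation is a single-visit comparison, so one stage effect held constant over visits would not fully adjust Month 12 if that effect changes with time. And if only 10% are later stage (6 of 60), there is a 25% chance of no such control and a 66% chance of at most one. The adjustment would then rest mostly on the BioBridge arm.

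None of this argues against prespecifying the covariate, because the cost is so small.

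**Conclusion.** The point holds as a recommended improvement in precision and as protection against an unlucky allocation. Stage is unrestricted above II, must be judged at screening, and appears in neither the randomization nor the model. The plan is valid without it.

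Over assumed ranges of 10 to 50% later than Stage II and a 5 to 20 point lower response, power at 20 points runs from 0.890 to 0.962 against 0.894 unadjusted. The detectable difference runs from 20.3 down to 17.3 points against 20.2. The gain is small at D of about 10 points or less and material only at about 15 to 20. These figures rest on p and D, which the documents do not supply, on a total SD of 19, and on the Month 12 comparison standing in for the full mixed model.

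**What to change.** - Record the actual ISL stage (II, or later than II) before randomization, on the checklist or case report form, and add it to the study calendar. A Yes to item 7 does not carry the value into the dataset.
- Prespecify stage as a baseline fixed effect in the 12.4 model. Include a stage-by-visit term, or otherwise confirm that the Month 12 contrast is adjusted. Use the same model for the secondary endpoint.
- Report the unadjusted result alongside, and tabulate stage by arm.

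Cost: one recorded value that screening already requires staff to determine, and one degree of freedom, or four with stage-by-visit (one main effect plus three interactions for the four visits). The power loss is negligible if stage turns out not to be prognostic. Eligibility, treatment and sample size do not change.
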